9.1 Sample Size and Randomization

We will examine data across 4 clinics in order to assess the feasibility of a multi-site study. We selected 25 dyads per clinic as our sample size (primary study sample- total n=100 PLWD), and their caregiver (n=100) in order to have the ability to examine feasibility measures within clinic as well as across clinic with some accuracy. For example, the degree of accuracy around an enrollment rate of 75% overall is 18% (width of the 95% confidence interval), allowing us a tighter margin of error overall. Within clinic, accuracy is larger (width of 95% confidence interval 36%), suggesting more uncertainty, but allowing us to examine clinic-specific enrollment to ensure that there is consistency across clinics.

To determine the feasibility of ascertaining and analyzing the primary (psychotropic medication use) and secondary clinical outcomes (hospitalizations, ED visits and nursing home placement of PLWDs) from the existing health system-wide electronic medical record (EMR) participants (the primary study sample of PLWD n=100) will be measured after the 6-month DICE implementation period using the EMR and compared to corresponding outcomes for the four participating clinics in the 6 months prior to the intervention (historical controls n=100); all PLWD in the four participating clinics), (N=300).

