Aim 2: Secondary clinical outcomes will be the feasibility of measuring rates of hospitalizations, ED visits and nursing home placement ascertained from the EMR. Mean PLWD participant health care utilization during the intervention period will be compared to historical controls (mean rate in the 6 months prior to the intervention). The feasibility of obtaining the nursing home placement variable from the EMR will be established during this pilot study by ascertaining nursing home placement from care partners and then determining if it subsequently is recorded in the EMR.

Interventions and Duration

The DICE Approach intervention will be piloted for 6 months during the study period. As above, mean PLWD participant psychotropic medication use during the intervention period will be compared to historical controls (mean rate of medication use among PLWD for the four participating clinics in the 6 months prior to the intervention). Secondary clinical outcomes(Aim 2) will be the feasibility of measuring rates of hospitalizations, ED visits and nursing home placement ascertained from the EMR. Mean PLWD participant health care utilization during the intervention period will be compared to historical controls (mean rate in the 6 months prior to the intervention).

Sample Size and Population

Study aim 1: We will examine data across 4 clinics to assess the feasibility of a multi-site study. We selected 25 dyads per clinic as our sample size (total n=100) to have the ability to examine feasibility measures within clinic as well as across clinic with some accuracy. For example, the degree of accuracy around an enrollment rate of 75% overall is 18% (width of the 95% confidence interval), allowing us a tighter margin of error overall. Within clinic, accuracy is larger (width of 95% confidence interval 36%), suggesting more uncertainty, but allowing us to examine clinic-specific enrollment to ensure that there is consistency across clinics.

An exploratory analysis will the subjects enrolled in the study (n= 100 PLWD) as described above, will be compared on [measures] with historical controls (n=100 PLWD) .

STUDY TEAM ROSTER

Principal Investigator: **[name]** – Joe P. Tupin Endowed Professor and Chair of the Department of Psychiatry and Behavioral Sciences at University of California, Davis (UC Davis)

[name]
[name]
Office [contact]
Main [contact]
[contact]

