3 STUDY DESIGN

There are no public-facing marketing materials for this study.

In this study, we will refine and pilot the application of DICE in 4 primary care clinics by: (a) leveraging existing clinic staff to deliver DICE to care partner-PLWD dyads; (b) using electronic resources to identify and recruit PLWD-care partner dyads based on clinically relevant and minimum inclusion/exclusion criteria; and c) evaluating clinically relevant outcomes using the electronic medical record (EMR). DICE will be implemented in four large primary care clinics within the UCD Health System over a 6-month period (n=100 PLWD, care partner n= 100) dyads; 25 dyads per site, allowing comparison of implementation and outcomes by site characteristics). Key “study champions” at each of the four primary care clinics will be licensed practical nurse assigned to each clinic who will serve as the Onsite DICE Coordinator (ODC).

Secondary outcomes: EMR data collection: To determine the feasibility of ascertaining and analyzing the primary (psychotropic medication use) and secondary clinical outcomes (hospitalizations, ED visits and nursing home placement of PLWDs) from the existing health system-wide electronic medical record (EMR) which will subsequently be used in a full-scale effectiveness ePCT. Clinical outcomes for PLWD participants will be measured after the 6-month DICE implementation period using the EMR and compared to corresponding outcomes for the four participating clinics in the 6 months prior to the intervention (“historical control” n=100; compared to the sample of PLWD n=100. The total study sample size N= 100.

As a minimal risk study embedded in primary care practices, we plan to obtain a waiver of informed consent for PLWD, care partners and clinic staff in order to reduce introduction of artificial care resources or biases wherever possible. Additionally, a HIPAA waiver will be obtained for subject identification (see a. below) and outcome ascertainment from the EMR. There will be minimal PHI data collected.

We will work with each clinic site to allow ODC’s the dedicated time (at least 6 hours) to engage in the online training during month one of the study. Because we want to have the least impact

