4 SELECTION AND ENROLLMENT OF PARTICIPANTS

Study Population: English-speaking (as discerned from the EMR) PLWD-Care partner dyads from the 4 participating clinics will be recruited. Dyads in the participating clinics will be identified in the following way:

- via warm handoff from a clinic provider to the ODC via the current standard of care for working with caregivers of PLWD regarding behavioral concerns, ODCs will be notified of the potential study participant by either of the two methods of ascertainment by the study RA. The ODC will then contact the care partner who is identified in the EMR as the responsible person or family member for the PLWD by telephone participation in the DICE program. We will also track the proportion of PLWD without a caregiver listed for study tracking.

Setting: Participants will be recruited from four primary care clinics in the Primary Care Network (total of 13) at University of California Davis. Clinics have been selected for the number of PLWD seen annually in each clinic. Below is preliminary information obtained on the potential subject population for the four study clinics from FY 1/1/2021-12/31/2021:

	Midtown	Elk Grove	ACC	FCC
>65 years old Dementia	63	67	66	76
Race/ethnicity				
White	40 (63.55)	35 (52.2%)	40 (63.5%)	27 (35.5%)
Black	11 (17.5%)	14 (20.9%)	11 (17.5%)	11 (14.5%)
Asian	8 (12.7%)	10 (14.9%)	8 (12.7%)	25 (32.9%)
Other	4 (6.4%)	8 (11.9%)	4 (6.3%)	
				13 (17.1%)

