9.5 Data Analyses

Data will be summarized with descriptive statistics to allow us to review the demographics and clinical characteristics of our enrolled participants, as well as to review implausible values. The extent of missing data will also be assessed as a key indicator of feasibility of collecting data from clinic notes and the EMR; additionally, we will ascertain whether baseline characteristics are associated with missingness in order to modify study procedures for the larger trial. Feasibility will be characterized by rate of enrollment (# enrolled/# invited to enroll), number of contacts between ODCs and dyads (summarized as averages/SDs across dyads), and time requirements (summarized as averages/SDs). We will examine these overall and by clinic, to ensure consistency across clinics. We will summarize data on medication use (binary: psychotropic use or not) for the four clinics overall prior to the study and for enrolled PLWD post-intervention and will compare them using mixed models with a logit link to analyze these pre-post data, accounting for correlation within clinic. Models will first be fitted in a crude fashion, secondarily we will include covariate adjustment as a means to inform design characteristics in the ePCT, recognizing we have limited power to make definitive conclusions from these analyses. We will similarly examine healthcare utilization (counts of hospitalizations and ED visits; binary measure of nursing home placement) once we ensure that these data are feasibly collected from the EPIC EHR.

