Models will first be fitted in a crude fashion, secondarily we will include covariate adjustment to inform design characteristics in the ePCT, recognizing we have limited power to make definitive conclusions from these analyses. We will similarly examine healthcare utilization (counts of hospitalizations and ED visits; binary measure of nursing home placement) once we ensure that these data are feasibly collected from the EPIC EHR. In order to go on to the ePCT, we must meet two criteria. First, the primary feasibility outcome (enrollment rates) must be greater than 75%. Second, we must be able to show that the lower limit of the 90% confidence interval for testing the pre-post medication use is greater than a 25% decrease in the pre-study proportion. The former criteria is based on the observed enrollment rate in the pilot from the WeCareAdvisor study (17) of PLWD-care partner dyads; the latter is based on what is reasonable to assume will change in the shorter 6-month pilot and is clinically relevant.

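### The enrolment-rate interval widths in Section 9.1 (18% overall, 36% per clinic) use the enrolled counts as denominators; with the invited as denominator, as Section 9.5 requires, they are about 15% and 31%

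*Combined protocol and SAP*

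**What the plan says.** Section 9.1 sets the sample at 25 dyads in each of four clinics ("primary study sample- total n=100 PLWD") and supports it with the precision of the enrolment rate: "the degree of accuracy around an enrollment rate of 75% overall is 18% (width of the 95% confidence interval"). For a single clinic it adds: "Within clinic, accuracy is larger (width of 95% confidence interval 36"%). The Précis, under Sample Size and Population, gives the same figures. Neither place names an interval method.

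The plan treats the 100 as participants. The Précis refers to "the subjects enrolled in the study (n= 100 PLWD"), and Section 3 carries the same 100 into the EMR comparison with historical controls ("compared to the sample of PLWD n=100").

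Section 9.5 defines the measure as "rate of enrollment (# enrolled/# invited to enroll"). It also makes this rate the primary feasibility outcome and requires it to exceed 75% before the larger trial goes ahead. The number of dyads to be invited is not stated anywhere.

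**The concern.** The denominator of a rate defined as enrolled over invited is the number invited. Section 9.1 appears to have used the number enrolled, which is the numerator, in its place. If so, the printed widths describe a different quantity from the one Section 9.5 will estimate.

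Two things are at stake. The widths are the only numerical argument for 25 dyads per clinic, and they concern the outcome that carries one of the two progression criteria. The number of invitations also determines both the precision of that outcome and the recruitment workload, and a feasibility pilot should state it.

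**Working it through.** **Inputs**
- Enrolment rate 75%; 95% widths of 18% and 36%; 25 dyads per clinic, 100 in total (Section 9.1 and Précis).
- Rate = number enrolled / number invited (Section 9.5).
- Number invited: not stated, so derived below from the 75% rate.
- Dementia counts by clinic, 2021: 63, 67, 66 and 76 (Section 4).

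**Formula.** For x enrolled out of n, the exact (Clopper-Pearson) 95% limits are the 2.5% quantile of Beta(x, n − x + 1) and the 97.5% quantile of Beta(x + 1, n − x). The width is upper minus lower.

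**Step 1: reproduce the plan's figures.** Widths in percentage points at 75%, with n = 100 and n = 25 (x = 18.75):

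| Method | n = 100 | n = 25 |
|---|---|---|
| Exact | 17.8 (65.3% to 83.1%) | 36.2 (35.8 for 19/25) |
| Wilson, continuity-corrected | 17.7 | 35.7 |
| Wald | 17.0 | 33.9 |
| Wald, continuity-corrected | 18.0 | 38.0 |
| Wilson | 16.8 | 32.3 |

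The exact and continuity-corrected Wilson intervals round to both printed values. The other three do not match both.

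**Step 2: derive the number invited.** 100 / 0.75 = 133.3 overall and 25 / 0.75 = 33.3 per clinic.

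**Step 3: recompute on the invited denominator**

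| Enrolled / invited | Exact width | Wilson, continuity-corrected |
|---|---|---|
| 100 / 133 | 15.3 (67.0% to 82.3%) | 15.3 |
| 25 / 33 | 31.2 (57.7% to 88.9%) | 30.9 |

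Rounding the invited up to 134 and 34 gives exact widths of 15.4 and 31.5.

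**Step 4: check dependence on the 75%.** Hold enrolment at the planned numbers and vary the number invited.
- 100 enrolled, 111 to 272 invited (rates of 90% down to 37%): the largest exact width is 15.6, at 148 invited. Examples are 12.0 at 100/111 and 14.3 at 100/200.
- 25 enrolled, 28 to 76 invited: the largest exact width is 31.8, at 37 invited.

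The printed 18 and 36 are not reached at any rate in these ranges.

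**Step 5: set the invited number against the patient pool.** 63 + 67 + 66 + 76 = 272. Then 133 / 272 = 49%, and 33 per clinic is between 33/76 = 43% and 33/63 = 52% of a clinic's count. The pool is a one-year count taken before the care-partner and English-language criteria, so it is only a rough ceiling.

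**The case against.** - **The printed arithmetic is correct for n = 100 and n = 25, and it is offered as an example.** Both points are true. The fault is the choice of denominator, not the calculation. It is nonetheless the only numerical support for the sample size.
- **The 100 and 25 may have been meant as dyads invited.** The sizing sentence in Section 9.1 does not itself say enrolled. On that reading the widths stand, but a 75% rate would then enrol about 75 dyads, or about 19 per clinic. That contradicts the 100 dyads and 25 per site stated throughout, and the word enrolled in the Précis. One statement has to change on either reading.
- **The method is inferred.** A Wald interval with about 90 overall and 22 to 23 per clinic gives similar widths (17.9; 36.2 to 35.4). Those counts appear nowhere in the plan, whereas 100 and 25 do.
- **15% may be optimistic overall, because dyads within a clinic may be correlated.** This stands as a caution. Widening 15.3 to 18 takes a design effect of (18 / 15.3)² = 1.38. With 33 invited per clinic, that is an intraclass correlation of 0.38 / 32 ≈ 0.012; the plan gives no value. However, the printed 18% is itself reproduced by treating dyads as independent, so correlation does not explain it. It also has no bearing on the within-clinic 36%.
- **The plan does not say who counts as invited.** Recruitment is by warm handoff from a clinic provider followed by a call from the coordinator, under a consent waiver. This also stands, and it is a further reason to state the denominator.

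**Conclusion.** The concern holds. The widths in Section 9.1 and the Précis do not describe the rate that Section 9.5 defines. On that definition, with 100 enrolled at 75%, they are about 15 points overall (not 18) and about 31 per clinic (not 36).

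These values rest on the exact interval, or the continuity-corrected Wilson, which are the methods that reproduce the plan's own figures. They also take 100 and 25 as the enrolled counts and treat dyads as independent. A Wald interval would give about 15 and 29.

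The matter is minor. The printed precision is conservative, so it does not show that the sample is too small. The progression criterion compares the rate with 75% and does not use the interval width.

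**What to change.** In Section 9.1 and in the Précis, state the expected number invited, name the interval method and restate the widths. Suggested text:

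*If 100 dyads are enrolled (25 per clinic) at an enrollment rate of 75%, about 133 will be invited (about 33 per clinic). The exact (Clopper-Pearson) 95% confidence interval for enrolled/invited is then about 15 percentage points wide overall and about 31 within a clinic. The overall width assumes independent dyads and would be wider with within-clinic correlation.*

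If the sponsor used another interval method, name it and give its widths. It would help to say in the same place which contact counts as an invitation.

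The cost is wording in two places. No dyads are added, and the sample of 100, the Section 9.5 analysis and the progression criterion do not change. The one drawback is that 15% looks tighter than clustered data may allow, so the independence note must stay with it.

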9.2 Treatment Assignment Procedures

Not applicable

9.3 Interim analyses and Stopping Rules

Not applicable

9.4 Outcomes

Clinical outcomes: all UCD clinical sites (inpatient and outpatient) use the same EMR (EPIC), so ascertaining clinical outcomes will be uniform across clinics. The primary clinical outcome is the feasibility of measuring psychotropic medication use. Mean PLWD participant

psychotropic medication use during the intervention period will be compared to historical controls (mean rate of medication use among PLWD for the four participating clinics in the 6 months prior to the intervention). Secondary clinical outcomes will be the feasibility of measuring rates of hospitalizations, ED visits and nursing home placement ascertained from the EMR. Mean PLWD participant health care utilization during the intervention period will be compared to historical controls (mean rate in the 6 months prior to the intervention). The feasibility of obtaining the nursing home placement variable from the EMR will be established during this pilot study by ascertaining nursing home placement from care partners and then determining if it subsequently is recorded in the EMR.

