7.3 Adverse Events and Serious Adverse Events

Adverse Event (AE): Any untoward or unfavorable medical occurrence in a clinical research study participant, including any abnormal sign (e.g. abnormal physical exam or laboratory finding), symptom, or disease, temporally associated with the participants' involvement in the research, whether or not considered related to participation in the research.

Serious Adverse Event (SAE): Any adverse event that:

- Results in death
- Is life threatening, or places the participant at immediate risk of death from the event as it occurred
- Causes persistent or significant disability or incapacity
- Results in congenital anomalies or birth defects
- Is another condition which investigators judge to represent significant hazards

No AE's or SAE's are expected based upon the study intervention. Hospitalizations and ED visits are secondary outcomes in the study and not considered adverse events. However, we will collect data on such events from the medical chart and caregiver report during visits and report them as needed.

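### A missing-data tally cannot show whether the UCD EMR misses hospitalizations and ED visits at outside facilities, and the care-partner check that could is planned only for nursing home placement

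*Combined protocol and SAP*

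**What the plan says.** Section 9.4 (Outcomes) defines the secondary clinical outcomes: "Secondary clinical outcomes will be the feasibility of measuring rates of hospitalizations, ED visits and nursing home placement ascertained from the EMR". Its support for EMR ascertainment is that "all UCD clinical sites (inpatient and outpatient) use the same EMR (EPIC), so ascertaining clinical outcomes will be uniform across clinics".

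For nursing home placement the same section adds an external check: "ascertaining nursing home placement from care partners and then determining if it subsequently is recorded in the EMR". It describes no such check for hospitalizations or ED visits.

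Section 9.5 (Data Analyses) gives the indicator of EMR feasibility: "The extent of missing data will also be assessed as a key indicator of feasibility of collecting data from clinic notes and the EMR". The utilization outcomes take the form "counts of hospitalizations and ED visits; binary measure of nursing home placement", to be examined "once we ensure that these data are feasibly collected from the EPIC EHR". No method or threshold for ensuring this is given. Section 9.5 also says "In order to go on to the ePCT, we must meet two criteria"; the two are enrollment and medication use.

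Section 7.3 (Adverse Events and Serious Adverse Events) says of hospitalizations and ED visits that "we will collect data on such events from the medical chart and caregiver report during visits and report them as needed". Nothing connects those caregiver reports to Aim 2b.

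**The concern.** For these two outcomes, capture is the result Aim 2b seeks. A shared EMR across UCD sites supports uniform recording of UCD care. It does not show that care at another hospital or ED reaches the record. A person whose outside admission was never recorded looks the same in the data as a person who was not admitted.

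Section 8 makes this more than theoretical. PLWD who leave routine outpatient care remain in follow-up, and some may then be treated elsewhere.

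At stake is the feasibility finding itself. The pilot could report complete utilization data while an unknown share of events is unseen. The sponsor already uses the right method for nursing home placement, and the documents give no reason for leaving the other two outcomes out.

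**Working it through.** **1. The plan's own figure.** The plan gives no number for EMR capture. Its only precision figures are 95% CI widths of 18% (n = 100) and 36% (n = 25) around a 75% enrollment rate (Section 9.1). The exact (Clopper-Pearson) method reproduces them: 75/100 gives 17.8% and 19/25 gives 35.8%. The point does not rest on these figures, but the exact method is used below for consistency.

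**2. Why missingness cannot detect the loss.** Let c be the share of true events that appear in the EMR.
- Observed count = c × true count.
- Relative shortfall in the rate = 1 − c.
- Formal missingness = 0% for every c, because absence of a record is a count of 0.

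The documents do not give c. Over an assumed range:
- c = 0.9: rates 10% too low
- c = 0.5: rates 50% too low

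**3. In events.** Take 100 participants (Section 9.1), an assumed 0.2, 0.4 or 0.6 events per person over 6 months, and c = 0.8.

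| True events | Seen | Uncounted | Formal missingness |
|---|---|---|---|
| 20 | 16 | 4 | 0% |
| 40 | 32 | 8 | 0% |
| 60 | 48 | 12 | 0% |

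**4. What a caregiver-versus-EMR check would deliver.** Exact 95% CIs for capture, treating events as independent and every true event as reported by the caregiver:
- 16/20: 56% to 94%
- 32/40: 64% to 91%
- 48/60: 68% to 89%
- 21/30 (assumed, 70% capture): 51% to 85%

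Repeat events in one person would make these intervals too narrow. By clinic, 30 events over 4 clinics is 7.5 each; 5/7 gives 29% to 96% and 6/8 gives 35% to 97%. The check can expose a sizeable overall loss. It cannot compare clinics.

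**5. Effect on the historical comparison.** With no true effect, the apparent rate ratio is c(participants) / c(controls).
- Equal capture: 0.8/0.8 = 1.00, no distortion.
- If calls raise recorded events among participants only: 0.9/0.7 = 1.29, a spurious increase.

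The second case could arise because coordinators chart each DICE step in the EMR (Section 5.1), while controls are described only through EMR access (Section 6.2.1).

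**The case against.** The strongest reply is that the documents never say outside events go unrecorded. Coordinator notes are part of the EMR, so an admission mentioned on a call could be charted there. Section 7.3 already plans two sources, the chart and the caregiver. Missing data is described as one key indicator, not the sole test. The uniformity sentence concerns consistency between clinics, not completeness. All of this stands, and it limits the claim to events that may not be recorded.

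A reader might infer four stronger things, none of which the documents support:
- **Outside events leave no trace in the EMR.** The documents are silent on outside records.
- **The pilot would declare Aim 2b feasible.** There is no decision rule; the most that can be said is that the check could not reveal a loss.
- **The full trial would be sized on understated rates.** Nothing says it will be sized on utilization, and the primary clinical outcome is psychotropic use.
- **Capture differs by clinic.** There is no evidence either way, and the pilot is too small to test it.

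It can also be said that equal loss in both periods leaves the pre-post ratio intact. That is correct if the loss is equal, but it does not tell anyone whether utilization can be measured. Finally, caregiver report is not a gold standard, exists only for enrolled dyads, and under Section 7.3 is passed on only as needed. Those limits shape the remedy; they do not remove the gap.

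**Conclusion.** The concern holds in a limited form. Hospitalizations and ED visits at non-UCD facilities may not be recorded in the UCD EMR, and the planned missing-data assessment could not show it because an unrecorded event is scored 0. Aim 2b would then be unanswered for two of its three outcomes.

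The size is unknown. A 10% to 50% understatement follows only from the assumed 50% to 90% capture. These are secondary outcomes and neither go criterion depends on them, so this is a worthwhile, low-cost improvement and not a threat to the pilot's main conclusions.

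**What to change.** 1. In Section 9.4, extend the nursing home check to hospitalizations and ED visits. At each existing coordinator contact, ask a standard question about any hospitalization or ED visit and whether the facility was UCD.
2. For each reported event, record whether it appears in EMR encounter records. Do not count coordinator notes, since the caregiver's report may itself have created that entry.
3. In Section 9.5, report the overall proportion of caregiver-reported events found in the EMR as part of the Aim 2b result, with a 95% CI that allows for repeat events within a person. Give clinic-level counts descriptively only. State that caregiver report is not a gold standard and covers participants only.
4. Limit the uniformity statement to care delivered at UCD sites.
5. Keep the comparison with historical controls on the same structured encounter fields in both periods, adding neither caregiver-reported events nor events known only from coordinator notes.
6. Reconcile Sections 7.3 and 7.4, which say these events are not adverse events, with Section 7.5, which lists them as such. Also reconcile the schedule in Section 6.1 (hospitalizations and ED visits at Visit 7 only) with Section 7.3 (collected during visits).

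**Cost:** one standard question and one field per contact, some extra abstraction, and a few sentences of text. The estimate will be imprecise, and the feasibility result may be less favourable.
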